## G. Statistical Methods

### Power and Sample Size

**NOTE: our projected sample for the two CRC admissions is 180, reflected in the sample size calculations below which are based on typhoid vaccine administration. The protocol describes a sample of 240 because any screening participants who are ineligible and/or who elect not to continue are counted in the total by the IRB.**

Power calculations were based on previously published data estimating the effect of typhoid vaccine on inflammation (IL-6) and mood. Wright [56] evaluated both proinflammatory cytokine responses and mood following injection of typhoid vaccine or placebo in 30 healthy male volunteers. The effect of vaccine on IL-6 was large; at 3h the mean IL-6 in the vaccine group was 1.59 (SD=0.81) compared to 0.53 (SD=0.30) in the placebo group, yielding an effect size of Cohen's  $d = 1.5$ . The effect of vaccine on negative mood was also large, though smaller than the effect on inflammation. At 3h post-injection the mean negative mood was 12.8 (SD=7.7) in the vaccine group compared to 7.4 (SD=5.8) in the placebo group, yielding an effect size of  $d = 0.76$ . Based on these results, we expect the effect of vaccine on mood to be smaller than the effect on IL-6, thus power calculations were designed to ensure adequate sample size to detect effects of vaccine on mood, which will ensure adequate power for IL-6 as well.

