The three specific aims for the proposed study are to evaluate (1) the effect of cardiorespiratory fitness on vaccine response, (2) the effect of age and depressive symptoms on vaccine response, and (3) the moderating effect of fitness on the age- and depression-related effects on vaccine response. Since each woman will serve as her own control by receiving both the vaccine and the placebo injection, the corresponding hypotheses all involve complex interactions: (1) the two-way interaction between fitness and injection type (vaccine/placebo), (2) the two-way interaction between age/depression and injection type, and (3) the three-way interaction of fitness by age/depression by injection type. Sample size requirements are considerably higher for testing higher-order interaction terms, thus we based required sample size on the tests of the third specific aim: the three-way interaction between fitness, age/depression, and injection type, while ensuring adequate power for the first two aims as well. Throughout we assumed 2-tailed tests with an 0.05 level of significance and used SAS PROC GLMPOWER for calculations.

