**Table: Hypothesized group means for negative mood for power calculations**

VACCINE RESPONSE (SD=7.7)			PLACEBO RESPONSE (SD=5.8)			
	Low Depression	High Depression		Low Depression	High Depression	
High Fitness	10	15.2	12.6	High Fitness	8.5	9.1
Low Fitness	11.2	25.2	18.2	Low Fitness	8.7	9.3
Average	10.6	20.2	15.4	Average	8.6	9.2

These means yield effect sizes for the vaccine response of  $d = 0.73$  for the average effect of fitness and  $d = 1.25$  for the average effect of depression. Importantly, in line with Hypothesis 3, they yield an effect size for depression of  $d = 1.8$  for women with low fitness and a smaller effect of  $d = 0.68$  for women with high fitness. Additionally, we will have baseline (pre-injection) measures of outcomes which will be used as covariates in models. In an ongoing study of breast cancer survivors, baseline negative mood was highly correlated with subsequent measures throughout the day, with  $r = 0.79-0.85$ . Inflammatory markers were similarly highly correlated, with correlations of  $r > 0.9$ . To be conservative in the power calculations we assume a single covariate with a correlation of  $r = 0.75$ . **Based on these hypothesized means and one covariate, a sample of size  $n = 180$  will give us 81% power to detect the three-way interaction effect of fitness by depression by injection type on mood. We will also have 94% power for the two-way interaction of depression by injection type and >99% power for the two-way interaction of fitness by injection type.** As previously noted, effects on IL-6 are expected to be larger and group differences should be as big or larger, thus this sample size should provide us the ability to detect the effects on IL-6 as well.

These calculations are conservative for several reasons. As previously noted, our sample is older than the sample on which we base our estimates, thus we will likely see even larger effects and more dramatic effects of age, depression, and fitness and should have higher power. Additionally, power calculations were made assuming fitness and depression were dichotomized; we will obtain continuous measurements of these covariates and thus expect higher power. We will also collect serial measurements of outcomes over time and thus expect to have higher power than if we only obtained a single post-injection measurement.

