**Data Analysis Plan** Each subject will have two visits (vaccine, placebo), and within each visit the primary outcomes (inflammation, behavioral responses) will be measured before injection and then serially (every 90 minutes) over the subsequent ~7.5 hours. Primary data analyses will use area under the curve (AUC) to summarize within-visit inflammatory and behavioral responses for each outcome. Hierarchical linear regression models (HLMs) will then be used to capture within-subject correlation across the two visits. If significant effects are found, secondary analyses will use more complex multi-level HLMs to model the individual time points within visit in order to identify at what time in the post-injection period effects arise.

For Hypothesis 1, baseline relationships between cardiorespiratory fitness and inflammation and behavioral outcomes will be evaluated using HLMs; subjects will have two baseline measurements, one before each injection, so an HLM is needed to control for the within-subject correlation. Outcomes in these models will be baseline (pre-injection) inflammation, depressive symptoms, cognitive problems, pain, and fatigue, and predictors will include cardiorespiratory fitness and visit (first or second). Tests of the main effect of cardiorespiratory fitness will investigate baseline relationships between these variables. The effect of vaccine on these outcomes over time will also be investigated using HLMs. AUC for each outcome at each visit will be the dependent variable, and predictors will include injection type (vaccine/placebo), cardiorespiratory fitness, and their interaction, as well as the baseline (pre-injection) outcome level. Separate models will be fit for each of the primary outcome AUCs (inflammation, behavioral responses) and the effect of interest will be the two-way interaction of cardiorespiratory fitness by injection type (which is a between-subject\*within-subject interaction). This term will allow us to investigate differences in response for the vaccine compared to placebo (injection type effect) and how these differences differ by fitness level (cardiorespiratory fitness by injection type interaction).

For Hypothesis 2a, baseline relationships between inflammation and age as well as the effect of age on vaccine responses will be investigated using HLMs similar to those described for Hypothesis 1 with age

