replacing cardiorespiratory fitness. For Hypothesis 2b similar HLMs will again be used, with depressive symptoms replacing cardiorespiratory fitness. For Hypothesis 2c, the HLMs with inflammation and behavioral AUC responses as outcomes will be modified by including both age and depression and their interaction as predictors. The test of the age by depression interaction will test whether the combination of older age and high depressive symptoms produces greater responses than the effect of either alone.

HLMs with AUC for inflammatory markers as well as behavioral responses as outcomes will also be used to test Hypothesis 3. Predictors will include injection type (vaccine/placebo), cardiorespiratory fitness, and age or depression, as well as all interactions and the baseline outcome level. Separate models will be used to test moderation of age and depression effects. To test whether cardiorespiratory fitness moderates the effect of age/depression on outcomes we will test the three-way interaction of injection type by age/depression by cardiorespiratory fitness. This is a three-way interaction, and we note that the primary interest is actually in the contrast testing the age/depression by cardiorespiratory fitness interaction for the vaccine injection. The post-placebo information serves to reduce error variance by allowing each woman to serve as her own control.

In all models we will control for BMI and insulin resistance to avoid possible confounding. Additionally, secondary analyses will control for use of aromatase inhibitors or tamoxifen; by including these variables as covariates, we will assess whether these medications impact cardiovascular (i.e., blood pressure, HRV) and inflammatory responses to the vaccine. Separately, we will assess whether tamoxifen or aromatase inhibitor use is related to cardiovascular variables and inflammation at baseline.

In secondary analyses, we will also assess antidepressant use as a possible confounder and control for this in analyses. We note again that the crossover design allows each woman to serve as her own control, thus mitigating the effect of possible confounders.

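### A single slope for the visit-specific baseline can cost some precision in the injection-type interactions; splitting it into woman mean and visit deviation is an almost free improvement.

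*Combined protocol and SAP*

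**What the plan says.** In Section G, Data Analysis Plan, the dependent variable is the AUC of each outcome at each visit. For Hypothesis 1, "predictors will include injection type (vaccine/placebo), cardiorespiratory fitness, and their interaction, as well as the baseline (pre-injection) outcome level". For Hypothesis 3 the predictors are injection type, fitness and age or depression, "as well as all interactions and the baseline outcome level". The models for Hypotheses 2a to 2c are adapted from the Hypothesis 1 model.

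The same section recognises that the baseline is measured twice: "subjects will have two baseline measurements, one before each injection, so an HLM is needed to control for the within-subject correlation". That remark concerns the models in which baseline is the outcome. Where baseline is a covariate, the plan does not separate a woman's usual level from her deviation on the day, and it does not model baselines jointly with outcomes. One common slope is the natural reading, although the plan does not say so in words.

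Two kinds of contrast then rely on that slope. For Hypothesis 1, "the effect of interest will be the two-way interaction of cardiorespiratory fitness by injection type", which is a within-woman difference compared across fitness. For Hypothesis 3 the plan adds that "the primary interest is actually in the contrast testing the age/depression by cardiorespiratory fitness interaction for the vaccine injection", which compares different women.

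On correlations, Power and Sample Size reports that "baseline negative mood was highly correlated with subsequent measures throughout the day" (0.79-0.85 for mood, above 0.9 for inflammatory markers) and assumes 0.75. These are same-day values. No correlation between visits is given.

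**The concern.** The right slope for a vaccine-minus-placebo difference is the one relating a woman's change in baseline to her change in AUC. The right slope for comparing women is the one relating their average levels. If a stable trait links visits 10-30 days apart, which is plausible for mood and cytokines, the second slope is steeper than the first, and one fitted slope is a compromise between them. It is then too steep for the within-woman difference, which adds noise to the injection-type interactions, and too shallow for comparisons between women.

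The second effect can matter because women are randomised to sequence, not to fitness, age or depression. The Objectives themselves predict that these traits go with different pre-injection inflammation, and that fitness and depressive symptoms also go with different pre-injection fatigue. Incomplete adjustment in a simple contrast on such a trait would leave bias as well as noise.

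**Working it through.** **The plan's own figure.** The three-way contrast from the table of hypothesised means is [(25.2 - 11.2) - (15.2 - 10)] - [(9.3 - 8.7) - (9.1 - 8.5)] = 8.8. Power and Sample Size says "Throughout we assumed 2-tailed tests with an 0.05 level of significance and used SAS PROC GLMPOWER for calculations", and "our projected sample for the two CRC admissions is 180". With SD 7.7, r = 0.75 and eight independent cells of 22 (176 observations), the noncentrality is 8.8² / [7.7² × (1 - 0.75²) × 8/22] = 77.44 / 9.43 = 8.21. Power is 81.3%, against the stated 81%; with 180 observations it is 82.2%. So the 81% reproduces, but by treating 180 as independent observations rather than two visits per woman.

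**Slopes.** Let baseline and outcome have SD 1. Let r be the same-visit baseline-outcome correlation. Across visits, let c be the baseline-baseline, q the baseline-outcome and y the outcome-outcome correlation. Only r has a source in the documents; c, q and y are assumptions.

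- Within-woman slope: bW = (r - q)/(1 - c).
- Between-woman slope: bB = (r + q)/(1 + c).
- They are equal only if q = r × c.
- The single fitted slope is b = (wW·bW + wB·bB)/(wW + wB), where wW = (1 - c)/sW², wB = (1 + c)/sB², sW² = (1 - y) - 2b(r - q) + b²(1 - c) and sB² = (1 + y) - 2b(r + q) + b²(1 + c).

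**Example: r = 0.75, c = q = y = 0.6.** bW = 0.15/0.4 = 0.375 and bB = 1.35/1.6 = 0.844. At the solution sW² is about 0.395 and sB² about 0.481, so wW = 1.01 and wB = 3.33. Then b = (1.01 × 0.375 + 3.33 × 0.844)/4.34, about 0.73.

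**Precision of the injection-type interactions.** The residual variance of the visit difference is 2[(1 - y) - (r - q)²/(1 - c)] = 2(0.4 - 0.05625) = 0.6875 with the correct slope. One slope adds 2(1 - c)(b - bW)² = 0.8 × 0.358² = 0.103. The ratio is 1 + 0.103/0.6875 = 1.15; simulation of 180 women gave 1.12.

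**Simple between-woman contrast.** With a 0.5 SD baseline gap between groups, the part left over is (0.843 - 0.733) × 0.5 = 0.055 SD; simulation gave 0.057.

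Simulation results (1,500 replicates, r = 0.75, c = y = 0.6, gap 0.5 SD):

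| q | bW | bB | single b | extra interaction variance | left over in simple contrast | type I error, one slope / split |
|---|---|---|---|---|---|---|
| 0.40 | 0.875 | 0.719 | 0.824 | 1% | 0.056 SD, over-adjusted | 9-10% / 5% |
| 0.45 (= r × c) | 0.750 | 0.750 | 0.749 | none | none | 6-7% / 6% |
| 0.525 | 0.563 | 0.797 | 0.715 | 4% | 0.040 SD, under-adjusted | 7-8% / 5-6% |
| 0.60 | 0.375 | 0.844 | 0.733 | 12% | 0.057 SD, under-adjusted | 10-12% / 4-5% |

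At same-day correlations nearer the documented values, with q = c, the extra variance was 11% (r = 0.82, c = 0.6), 14-23% (r = 0.82, c = 0.7) and 10-24% (r = 0.90, c = 0.7-0.8). Over a wide grid with q at or above r × c, the median was 1-3% and the 95th percentile 19-33%. Injection-interaction estimates were unbiased throughout, with type I error of 4-7% under one slope.

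**Consequence for power.** On the plan's own scale, 3%, 10% and 20% more variance turns 81% into 80%, 77.5% and 74%, and keeping the precision of 180 women would take 185, 198 and 216. With two visits per woman and 45 women per group, the example gives a residual variance of 7.7² × 0.6875 × 1.15 = 46.9, so SE = √(4 × 46.9/45) = 2.04 and 8.8/2.04 = 4.3. Power is still about 99%.

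**Contrasts that are products of two between-woman factors.** With baseline gaps of 1.0 SD for depression and 0.5 SD for fitness and no baseline interaction, the vaccine-only fitness-by-depression contrast had bias -0.001 under either model. Type I error was 5.3% with one slope and 5.1% with two.

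**The case against.** The strongest reply is that this is a standard covariate-adjusted crossover model, that its main tests remain valid, and that the loss rests on cross-visit correlations supplied by the review. All of that stands. If q = r × c the split changes nothing, and if q is lower, under-adjustment becomes over-adjustment. A steeper slope between women is plausible but not documented.

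A reader might infer that the Hypothesis 2c age-by-depression test, or the vaccine-only age/depression-by-fitness contrast, leaves a fixed share of baseline differences unadjusted. The documents do not support this. Both are interactions of two between-woman factors, and a wrong baseline slope biases them only if baseline shows the same interaction. The Objectives predict separate baseline associations for each trait; they predict joint effects only for vaccine responses.

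The split is also not a complete cure. The mean of two baselines still measures the stable trait with error. In a simulation with a 0.5 SD interaction built into baseline, bias fell from 0.119 to 0.059, not to zero. Finally, the simple between-woman contrasts for which type I error rises are not the tests the plan names as of main interest for the AUC models; they would arise when an interaction is broken down by condition.

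What the reply does not remove is the asymmetry. The data are already collected, and the split costs under 1% in precision when the slopes are equal.

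**Conclusion.** The point holds as a conditional, low-cost improvement and not as an error in the plan. When a stable trait links the visits, one slope adds about 2-20% to the variance of the fitness-, age- or depression-by-injection estimates, with single scenarios reaching 24%. The size rests on assumed values of c, q and y, on equal SDs in the two conditions, and on same-day correlations for single readings standing in for those with AUC.

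Two further readings would go too far. The injection-type interactions are not biased. Nor is the trial left underpowered for its hypothesised three-way effect, which keeps at least 99% power under the crossover variance in the main scenarios examined.

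The adjustment error is confined to simple contrasts of fitness, age or depression when the groups differ at baseline, and its sign depends on q. With a 0.5 SD gap and q above r × c, the simulations left 0.02-0.08 SD and raised type I error to about 7-19%.

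**What to change.** In every AUC model for Hypotheses 1 to 3, replace the single baseline term by two prespecified covariates: the mean of the woman's two pre-injection values, and the visit's pre-injection value minus that mean. State how a woman with only one completed visit is handled; modelling baselines and outcomes jointly is an alternative that covers this case. The mean uses the second baseline, taken 10-30 days after the first injection, so like the present term it assumes negligible carry-over.

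The cost is one degree of freedom and a sentence or two in the Data Analysis Plan, with no new data. It should be fixed before unblinding, so that the form of adjustment is not chosen after seeing the results. Reporting the correlations between visits would show afterwards how much the split mattered.

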### OBJECTIVES

**Specific Aim 1:** To evaluate the relationships between cardiorespiratory fitness and inflammatory and behavioral responses (negative mood, fatigue, pain, and cognitive problems) to typhoid vaccine. **Hypothesis 1:** Prior to the vaccine or placebo, better cardiorespiratory fitness will be associated with lower levels of inflammation, depressive symptoms, fatigue, pain, and cognitive problems. The vaccine will produce larger inflammatory responses and greater negative behavioral changes than the placebo. Better cardiorespiratory fitness will attenuate the magnitude and duration of both proinflammatory and behavioral responses to the vaccine.

**Specific Aim 2:** To determine the effects of age and depressive symptoms on inflammatory and behavioral responses to typhoid vaccine and placebo. **Hypothesis 2a:** Compared to younger women, older women will have higher levels of inflammation prior to vaccine or placebo. Aging will amplify the inflammatory and behavioral responses to typhoid vaccine, with older women showing more enhanced and prolonged responses than younger women. **Hypothesis 2b:** Prior to the vaccine or placebo, women with higher levels of depressive symptoms will have higher levels of inflammation than less depressed women, as well as higher levels of fatigue. Depressive symptoms will intensify vaccine responses, such that women who are more depressed will produce larger and longer-lasting proinflammatory and behavioral responses to the vaccine than women who are less depressed. **Hypothesis 2c:** The combination of older age and high depressive symptoms will produce greater and longer-lasting increases in inflammation and negative behavioral responses to typhoid vaccine than either alone.

**Specific Aim 3:** To assess the ability of cardiorespiratory fitness to moderate age- and depression-related responses to typhoid vaccine. **Hypothesis 3:** Women with better cardiorespiratory fitness will show smaller age- and depression-related inflammatory and behavioral responses to typhoid vaccine.

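### Hypothesis 2c is about responses to typhoid vaccine, but its named test is age × depression averaged over the vaccine and placebo visits

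*Combined protocol and SAP*

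**What the plan says.** In Objectives, Hypothesis 2c says that older age combined with high depressive symptoms "will produce greater and longer-lasting increases in inflammation and negative behavioral responses to typhoid vaccine than either alone". The heading of Specific Aim 2 is wider: "To determine the effects of age and depressive symptoms on inflammatory and behavioral responses to typhoid vaccine and placebo". The hypothesis itself is stated for the vaccine only.

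The Data Analysis Plan in section G builds its models from a template given under Hypothesis 1. There, "AUC for each outcome at each visit will be the dependent variable". The predictors are injection type, fitness, their interaction and the pre-injection level, and "the effect of interest will be the two-way interaction of cardiorespiratory fitness by injection type". Hypotheses 2a and 2b reuse this template with age or depressive symptoms in place of fitness.

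For Hypothesis 2c the same models "will be modified by including both age and depression and their interaction as predictors". The test is then named: "The test of the age by depression interaction will test whether the combination of older age and high depressive symptoms produces greater responses" than either factor alone.

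For Hypothesis 3 the plan includes every interaction, names the three-way term with injection type as the test, and adds that the real interest is the contrast after the vaccine. The Power and Sample Size section says that "the corresponding hypotheses all involve complex interactions" and lists each one with injection type. For Aim 2 it lists only "the two-way interaction between age/depression and injection type".

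**The concern.** A claim about the response to vaccine needs a term that compares vaccine with placebo, or one confined to the vaccine visit. The named term does neither. Injection type, and its two-way interactions with age and with depression, can be read as carried over from the Hypothesis 1 template. The age × depression product is not crossed with injection type anywhere.

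Two things are at stake. Hypothesis 2c could be declared confirmed from an age × depression pattern that is the same after saline. And if there is no such pattern after saline, the reported coefficient is half the quantity the hypothesis is about. Power may also suffer, because the named term is a between-woman comparison and does not use the within-woman comparison that the crossover provides.

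**Working it through.** **1. What each term estimates.** Let I_V and I_P be the age × depression interaction in AUC at the vaccine and placebo visits. With both visits in the model and no three-way term:

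- written test: (I_V + I_P)/2
- three-way test: I_V − I_P

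If I_P = 0, the written term is I_V/2. If I_V = I_P, it equals I_V although nothing is specific to the vaccine. This is algebra and needs no assumed effect.

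**2. The plan's own figure.** The documents state no power for any age × depression test. The nearest figure is 81% for fitness × depression × injection type on mood. From the table of hypothesized means, the contrast is (25.2 − 11.2) − (15.2 − 10) − [(9.3 − 8.7) − (9.1 − 8.5)] = 14.0 − 5.2 − 0 = 8.8. Residual SD = 7.7 × √(1 − 0.75²) = 5.09. With 180 observations in eight cells (22.5 each), SE = 5.09 × √(8/22.5) = 3.04, and the noncentral F gives 82.2%. That treats the 180 as independent observations, which is a separate matter. The calculations below use 180 women with two visits each.

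**3. Two different truths, one answer.** Assume 45 women in each of four age/depression cells (180/4), the plan's SDs of 7.7 and 5.8, covariate correlation 0.75, and between-visit correlation ρ from 0 to 0.8 (not in the documents). The sum over visits has variance (1 − 0.75²) × (7.7² + 5.8² + 2ρ × 7.7 × 5.8) × 4/45. At ρ = 0.5 this is 0.4375 × 137.59 × 4/45 = 5.35, so SE = 2.31.

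| Assumed interaction (mood points) | Written test rejects | Three-way test rejects |
|---|---|---|
| 8.8 after vaccine, 0 after placebo | 93% to >99% | >99% |
| 4.4 after each | 93% to >99% | 5% |
| 2.2 after each | 41–63% | 5% |

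The first two rows have the same average (4.4), so the written test cannot tell them apart.

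**4. Allowing for baseline adjustment.** Trials were simulated with a REML random-intercept model, 1,500 per setting (2,000 for the null), n = 180. Assumptions: baseline–AUC correlation r = 0.75, 0.85 or 0.9 (the plan gives 0.75 for planning, 0.79–0.85 for mood and above 0.9 for inflammation); residual between-visit correlation ρ = 0, 0.25 or 0.5; between-visit baseline correlation 0.5; BMI and insulin resistance included but unrelated to outcome. The effect is equal on both injections.

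Two sizes were used. The larger is 0.2 SD per SD of age × SD of depression, which after median splits is 0.2 × (2√(2/π))² = 0.51 SD, or about 0.51 × 5.8 = 3.0 mood points. The smaller is a 0.2 SD high/low difference-in-differences, 0.2 × 5.8 = 1.2 points.

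| Written test rejects, by share of effect present at baseline | None | Half | All |
|---|---|---|---|
| Larger effect | 98.7–100% | 80–99% | 8–29% |
| Smaller effect | 20–55% | 11–19% | 5–6% |

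The three-way test rejects in 3.9–6.2% across all these settings. With no effect at all, the written test rejects in 4.1–5.8% and the three-way test in 4.5–5.9%.

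Hand check, smaller effect, none at baseline: SE = √[(1 − r²)(1 + ρ)/2 × 4/45]. At r = 0.75, ρ = 0.5 this is 0.171, z = 0.2/0.171 = 1.17, power about 21%. At r = 0.9, ρ = 0 it is 0.092, z = 2.18, power about 58%. Hand check, larger effect, all at baseline, r = 0.75, ρ = 0: about 0.2 × (1 − 0.75) = 0.05 remains; SE = √(0.4375 × 0.5/180) = 0.0349; z = 1.43, power about 30%. These agree closely with the simulations.

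**5. Effect on the vaccine visit only.** With an effect of 0.2 on that visit, the written coefficient averages 0.10 and the three-way coefficient 0.20. Power, written vs three-way:

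| Effect size | r | ρ = 0 | ρ = 0.5 |
|---|---|---|---|
| Larger | 0.75 | 77% vs 79% | 61% vs 97% |
| Larger | 0.9 | 98.4% vs 98.6% | 90.4% vs 100% |
| Smaller | 0.75 | 11% vs 13% | 8% vs 17% |
| Smaller | 0.9 | 16.9% vs 19.9% | 13.0% vs 33.6% |

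The pattern follows from the variances: with σ² = 1 − r², the larger-effect SEs are √[σ²(1 + ρ)/(2n)] for the written term and √[2σ²(1 − ρ)/n] for the three-way term. At r = 0.75, ρ = 0.5 they are 0.0427 and 0.0493, so z = 0.10/0.0427 = 2.34 (65%) against 0.20/0.0493 = 4.06 (98%).

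**The case against.** The strongest reply is that the wording is incomplete and the design itself is sound. The Hypothesis 2c model is a modification of one that already contains injection type, and the Power and Sample Size section presents all hypotheses as interactions with injection type. Crossing the new product term with injection type may well have been intended. That is possible, but it does not rescue the named test. In a full factorial, the two-way term is the average over injections under effect coding, or the effect at whichever injection is the reference under 0/1 coding. Under Hypothesis 3 the authors wrote the injection-type term out.

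The second reply is that the baseline covariate protects against a general age × depression difference. It does so in part: rejection falls to 5–29% if the whole effect is already present at baseline. It does not remove a difference that arises after baseline on both days, and each day includes a catheter, fasting, cold pressor and repeated testing. The plan's only table of hypothesized means sets the placebo-visit interaction to zero. That table is for fitness × depression, and under that pattern the harm is a halved coefficient and some loss of power, with no false confirmation.

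The third reply concerns the figures, and it stands as a limit on them. No age × depression effect is given. The SD of 5.8 is for mood at 3 hours and not for AUC. The quoted correlations are with measures through the day and not with AUC. The simulations in step 4 use equal variances at the two visits; step 3 uses the plan's unequal SDs and shows the same pattern.

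Finally, the vaccine-visit contrast could be made the primary test, since the plan calls the corresponding contrast its main interest under Hypothesis 3. Either choice would cure the omission; the present text names neither.

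**Conclusion.** The plan is wrong as written on this point. The test named for Hypothesis 2c does not address a vaccine-specific effect, and it is the only vaccine-response hypothesis whose named test leaves out injection type. That conclusion, and the halving when the placebo-visit interaction is zero, rest on the text and on algebra alone.

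The size of the error is not fixed by the documents. If the effect is equal after both injections, the written test's rejection rate runs from about the nominal 5% (small effect, wholly present at baseline) to essentially 100% (larger effect, arising after baseline). If the effect is confined to the vaccine visit, the power loss is slight when residuals at the two visits are uncorrelated and large when they are correlated at 0.5. One sub-hypothesis of Aim 2 is affected, and no stated sample size or power figure changes. It should be corrected before the analysis.

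**What to change.** In the Hypothesis 2c text of the Data Analysis Plan, state that the AUC model contains injection type, age, depressive symptoms and all their interactions, together with the baseline level and the covariates already specified. Name age × depression × injection type as the test of Hypothesis 2c, and report the age × depression contrast at the vaccine visit as follow-up. This is the model form the plan already uses for Hypothesis 3. Add the term to the effects listed for Aim 2 under Power and Sample Size, where only two-way terms now appear. The cost is a change of wording: same data, same model family, no change to study conduct.
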